On Day 0 participants will receive a single loading dose consisting of 2 injections, each of which will contain 120 mg of teverelix TFA (Group 1) or 180 mg teverelix TFA (Group 2). The first injection will be administered as an IM and the other as an SC injection (Stage 1).

After Stage 1, participants of Group 1 will receive a maintenance dose, which will consist of a single 120 mg SC injection administered every 42 days up to Day 168.

If treatment of Group 1 has been terminated early due to a low therapeutic response rate, recruitment of participants into Group 2 will start.

After Stage 1, participants in Group 2 will receive a maintenance dose, which will consist of a single 180 mg SC injection administered every 42 days up to Day 168.

The total treatment period in this study will end when the last maintenance dose is administered on Day 168.

For Group 2 subjects only a follow up period will be followed. Subjects will return on Day 203 (5 weeks after final Day 168 injection) for serum T levels to be measured. Weekly visits will continue until serum T levels are ≥ 1 ng/mL (local lab result).

A safety follow-up visit will be done 7days after serum T levels are ≥ 1 ng/mL (local lab result). Participants withdrawn early from the study will be asked to return to the study site for a safety follow-up visit ≥ 28 days after administration of the last dose.

Population

Inclusion Criteria

The participant must fulfil all of the following criteria:

- 1. Is male, aged \leq 85 years (\geq 18 years) at the beginning of the treatment period (Day 0)
- 2. Has histologically proven advanced adenocarcinoma of the prostate (metastatic or non-metastatic, hormone-sensitive, non-curative), suitable for androgen deprivation therapy
- 3. Is treatment naïve for any of the following:
 - a. GnRH analogues,
 - b. Androgen receptor antagonists, or
 - c. Androgen synthesis inhibitors (e.g. abiraterone)
- 4. Agrees to practice contraception during the entire study treatment period and for 3 months after the last dose of IMP is administered:
 - a. Either by using double barrier contraception,
 - b. or, is truly sexually abstinent, when this is in line with the preferred and usual lifestyle of the participant

Note: Periodic abstinence [e.g. calendar, ovulation, symptothermal, postovulation methods for the female partner with childbearing potential] and withdrawal are not

acceptable methods of contraception.

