3.1 Core Study

This is an adaptive Phase 2, open-label, multicentre study to evaluate the PK, PD, efficacy and safety of teverelix TFA, a GnRH antagonist in participants with advanced prostate cancer.

For Group 1, it is planned to enrol approximately 24 participants from 3 investigational sites in Lithuania to obtain 20 evaluable participants with prostate advanced cancer. For Group 2, it is planned to enrol approximately 60 participants from up to 7 investigational sites in Lithuania and (potentially) Netherlands/Belgium in order to obtain 50 evaluable participants with advanced prostate cancer, for the assessment of treatment response on Day 28 and throughout the study up to Day 168.

Figure 1 displays the study design.

The study consists of the following periods/visits:

Page 32 of 84

NTEV

Screening Period: Day -6 to -1 **Groups 1 & 2 Treatment Period:**

Stage 1: Loading dose administered at baseline (Day 0) with follow-up visits until Day 28

Stage 2: Maintenance treatment administered every 6 weeks with visits from Day 28 up to Day 168, or until treatment ceases to become effective

Follow-up Visit: 28 days after the last dose of IMP

Group 2 (Stage 3 subjects only) Treatment Period:

Stage 1: Loading dose administered at baseline (Day 0) with follow-up visits until Day 28

Stage 2: Maintenance treatment administered every 6 weeks with visits from Day 28 up to Day 168, or until treatment ceases to become effective

[figure not shown]
Stage 3: Follow up period. Day 203 visit followed by weekly visits until Day 252 or until serum T levels are ≥ 1 ng/mL (local lab result), whichever occurs first Follow-up Visit: Day 259 or ≥ 7 days after serum T levels are ≥ 1 ng/mL (local lab result), whichever occurs first

An overview of the Schedule of Assessments is provided in Section 7.1. After signing the informed consent for the core study, participants will undergo a screening examination within 6 days prior to the administration of teverelix TFA to verify the participants' eligibility, and to document participant characteristics, including medical and surgical history, and disease characteristics.

Table 1 presents the 2 dosing regimens to be evaluated in this study.

Figure 1: Study Design

TEVERELIX IN ADVANCED PROSTATE CANCER PHASE 2 **STUDY PROGRESSION**

ANT-1111-02, Teverelix TFA in Prostate Cancer

FINAL Version 5.0, 31 May 2022

Page 33 of 84

Table 1: Dosing Regimens under Evaluation

_Group	Loading Dose	Maintenance Dose	Dosing Interval

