All enrolled participants will be identifiable throughout the study. The investigator will maintain a personal list of participant numbers and participant names to enable records to be found at a later date.

Upon enrolment each participant receives a 5-digit screening number, which is sufficient for unambiguous identification:

Digits 1 and 2: Study centre (11, 12, 13, etc.)

Digits 3, 4 and 5: Individual participant number within the centre (consecutively in

the order of enrolment within the centre: 001, 002, etc.)

Enrolled participants who drop out of the study before their baseline visit will retain their screening number.

On completion of the screening phase, the participant's eligibility will be confirmed. Eligible participants will receive treatment on Day 0. All participants will receive the same dose per treatment group (Group 1 or Group 2) of teverelix TFA as defined in Section 5.1. Medication will be dispensed in numerical order, starting with the smallest number available in the centre.

5.4 **Selection of Doses in the Study**

The goal of this study is the selection of an optimal treatment regime, which allows achievement of the highest level of efficacy with an acceptable safety profile and optimal convenience for patients and physicians. For this reason, 2 treatment regimens will be evaluated.

The treatment regimen for Group 1 comprises a dose of 120 mg administered SC and IM as a loading dose and SC as a maintenance dose every 6 weeks. For Group 2, the dose will be 180 mg administered SC and IM as a loading dose and SC as a maintenance dose every 6 weeks. The 180 mg dosage has been administered in 4 Phase 1 studies conducted in healthy male volunteers and 2 Phase 2 studies conducted in participants with APC. No severe or serious AEs were noted in these studies. The dosing regimen and treatment period will be according to the details described in Section 5.1.

5.5 **Selection and Timing of Dose for Each Participant**

Participants will receive different doses depending on whether they join Group 1 or Group 2. The study will enrol participants into Group 1 first.

On Day 0 participants will receive a single loading dose consisting of 2 injections, each of which will contain 120 mg of teverelix TFA (Group 1) or 180 mg (Group 2). The first injection will be administered as an IM injection and the other as an SC injection (Stage 1).

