7.2.1 Screening Examination (Day -6 to Day -1)

At the screening examination the following will be carried out and/or documented:

- Participant signs ICF as a part of the written participant information including the agreement concerning protection of personal data and direct access to source documents
- Date of visit
- Demographic data (height, weight, year of birth, age)
- Diagnosis of study indication (specify duration, severity as requested)
- Relevant medical history for the past 5 years
- Pre-treatment during the past 6 months
- Concomitant disease(s) (including date of diagnoses), concomitant therapy(ies)
- Physical examination (see Section 6.3.2)
- 12-Lead ECG (see Section 6.3.3)
- Safety laboratory tests (fasted \geq 8 hours)
- Total T (local laboratory)
- HbA1c
- Vital signs
- Check of inclusion and exclusion criteria

Concomitant diseases are to be documented, taking into consideration the medical history of the participant for the past 5 years. Findings that are not medically relevant for the study are: operation scars, accident scars, and bad sight etc.

7.2.2 Baseline Examination (Day 0), Stage 1

At baseline examination the following will be carried out and/or documented:

- Date of visit
- Weight, and BMI
- Documentation of changes in concomitant diseases and/or concomitant therapies (also medication taken only once and any non-prescription medicine)
- AEs (for definition see Section 6.2.4)
- Check of inclusion and exclusion criteria
- Physical examination
- 12-Lead ECG
- Continuous 24 h, 12-lead Holter ECG (Subset of 30 Group 2 subjects only)
- Safety laboratory tests (fasted (≥8 hours))
- Vital signs
- Pre-dose blood sampling for PK, PSA and PD analysis
- Pre-dose blood sampling for cardiac biomarkers (Group 2 only)
- Administration of the loading dose of teverelix TFA, which consists of IM followed by SC injection
- ISI
- Post-dose PK blood sampling

Additional Visits for Pharmacokinetic and Pharmacodynamic Samplings during Stage 1:

- During Stage 1, the participant will return to the study site for additional PK and PD blood sampling at 24, 48 and 72 hours post-dose, and on Days 4, 7, 10, 12, 14, and 21
- On Day 21 local testing of T levels will be performed
- On Days, 7, 14, and 21, blood sampling for PSA will be performed

7.2.3 Treatment (Maintenance Dose) Period Visits (Day 28 to Day 168), Stage 2

At the treatment period visits, the following examinations will be carried out and/or documented:

- Date of visit

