#### **4.2.2      Adverse Events**

An adverse event (AE) is any untoward medical occurrence in a participant or clinical investigation participant who is administered a pharmaceutical product. This untoward medical occurrence does not necessarily have a causal relationship with the administered treatment. An AE can, therefore, be defined as any unfavourable and unintended sign (including abnormal laboratory findings), symptom, or disease that is temporally associated with the use of a medicinal (investigational) product, whether related to that medicinal (investigational) product.

AE data will be collected from the time that informed consent was given, for the duration of the trial.

Missing AE data will be handled according to the rules specified in Section 6.9.2.

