#### **4.2.3      Adverse Event Definitions**

For each AE, the investigator will document the following:

- **Signs and symptoms** of the event (if a specific disease can be diagnosed, this disease should be the reported AE; if only signs and symptoms can be evaluated, each sign or symptom should be reported as a separate AE)
- **Onset date and time** (if a change from pre-dose in a laboratory test is reported as an AE, the start date is the date of collection of the first laboratory sample that shows the change)
- **End date and time** (if a change from pre-dose in a laboratory test is reported as an AE, the end date is the date of collection of the first laboratory sample that shows a return to pre-dose level)
- **Measure taken** (none, drug treatment required, hospitalisation or prolonged hospitalisation, study discontinuation, other measures [specification])
- **Outcome** (recovered/resolved, recovering/resolving, recovered/resolved with sequelae, not recovered/not resolved, fatal, unknown)

In addition, each AE will be rated by the investigator according to the following categories:

- **Relationship to study medication:** Related, Probable, Possible, Unlikely, Not related. Investigator record from the eCRF will be reported.
- **Intensity:** Grade 1(mild), Grade 2 (moderate), Grade 3 (severe), Grade 4 (life-threatening), Grade 5 (death). This is based on National Cancer Institute (NCI) Common Terminology Criteria for Adverse Events (CTCAE), and investigator record from the electronic Case Report Form (eCRF) will be reported.
- **Seriousness:** Serious AEs reported from the time of informed consent until 31 days after the dose of study medication will be recorded on the eCRF.

Document:

C:\ProgramData\activePDF\Temp\DocConverter\API\Input\\$651f4dc0b253\$FE3041C5883446E892B20AB6D3F0E1BD.docx

Author: [name]

Version and Date: Version 1.0, 21 Apr 2023

Page 34 of 66

- **Expectedness:** Expected, Unexpected.

A treatment-emergent AE (TEAE) is defined as any new or worsening pre-existing AE with a date equal to or later than the date of IMP administration.

A treatment-emergent serious AE (TESAE) is defined as any new or worsening pre-existing SAE with a date equal to or later than the date of IMP administration.

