## **6. Statistical Analyses**

Both Group 1 and Group 2 outputs will be displayed and analysed separately. Combined totals of the groups will be displayed for completeness, but not analysed.

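### Treatment-emergent AEs have no end date, so crude AE percentages cover follow-up to Day 196 for some completers and to Day 210 to 259 for Group 2 men in Stage 3

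*SAP*

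**What the plan says.** **Definition.** SAP 4.2.3 defines a TEAE as "any new or worsening pre-existing AE with a date equal to or later than the date of IMP administration" and a serious TEAE in the same way. The protocol synopsis and Protocol 8.1.5 also give only a start.

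**Collection.** SAP 4.2.2 states: "AE data will be collected from the time that informed consent was given, for the duration of the trial". For seriousness, SAP 4.2.3 adds a limit: "Serious AEs reported from the time of informed consent until 31 days after the dose of study medication will be recorded on the eCRF". It does not say which dose is meant.

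**Follow-up.** For Groups 1 and 2 in general, Protocol 3.1 gives: "Follow-up Visit: 28 days after the last dose of IMP". The synopsis then adds Stage 3: "For Group 2 subjects only a follow up period will be followed". Protocol 7.2.5 lists AEs among the procedures at Day 203, at each weekly visit after that, and at the final assessment. Not every Group 2 man need have Stage 3, because the synopsis lets men enrolled under version 4.0 remain on it.

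**Reporting.** SAP 5.1.2 sets the per-subject AE denominator as the number of subjects in each arm. SAP 6.9.2 plans AE summaries with no split by stage and no exposure adjustment; only injection site reactions (SAP 6.9.2.1) are shown by visit and stage. The groups are presented separately, and SAP 6 adds: "Combined totals of the groups will be displayed for completeness, but not analysed".

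**The concern.** A crude incidence proportion can be read across groups only if the groups were watched for about the same time. Here a start-only definition is combined with AE collection for the whole trial, and Stage 3 lengthens the trial for part of Group 2 only. A Stage 3 man has up to eight more weekly AE enquiries and a later final visit, and any new event in that time enters the same percentage as an event on treatment.

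There are two consequences. The Group 1 and Group 2 percentages cover different windows, and the Group 2 percentage is itself a mixture of two follow-up lengths in proportions that the documents do not give. SAP 5.1.2 and 4.2.3.1 refer to a study period for AE counting, but neither defines one, so a programmer cannot tell whether a Day 240 event belongs in the main table.

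This matters although no test between doses is planned. Protocol 5.4 states: "The goal of this study is the selection of an optimal treatment regime", and makes an acceptable safety profile part of that goal. Protocol 8.1.12 says the Group 2 data are to support dose selection for Phase 3. The per-group TEAE percentages are a natural input to both judgements.

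**Working it through.** **Inputs** (nominal days, men who complete treatment)
- Last dose, both groups: Day 168 (synopsis, Treatment).
- No Stage 3: follow-up visit 28 days after last dose, ±3 days (Protocol 3.1 and schedule of assessments).
- Stage 3: first visit Day 203, then weekly to Day 252 at most; final assessment 7 days after local T reaches 1 ng/mL, or Day 259, whichever is first.
- Dosing interval: 42 days.
- SAE recording limit: 31 days after the dose, taken here as the Day 168 dose.

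**The plan's own figure.** Latest final assessment = 168 + 84 + 7 = Day 259, as stated.

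**Observation windows**
- No Stage 3: 168 + 28 = Day 196.
- Earliest Stage 3 exit: 203 + 7 = Day 210. Excess 210 − 196 = 14 days; ratio 210/196 = 1.07.
- Latest Stage 3 exit: Day 259. Excess 259 − 196 = 63 days; ratio 259/196 = 1.32.
- Intermediate case: T recovers 8 weeks after the last dose, 168 + 56 = Day 224, exit Day 231; ratio 231/196 = 1.18. Eight weeks is the upper end of the suppression that Protocol 1.2.2 reports for advanced prostate cancer. That figure refers to 0.5 ng/mL, not 1 ng/mL, so it is only a guide.

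**Effect on a crude percentage.** The documents give no AE incidence, so p, the incidence by Day 196, is assumed over a range. Under a constant hazard the percentage counted by day t is 1 − (1 − p)^(t/196). With all men completing and entering Stage 3:

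| Assumed p by Day 196 | Exit Day 210 | Exit Day 231 | Exit Day 259 |
|---|---|---|---|
| 10% | 10.7% | 11.7% | 13.0% |
| 30% | 31.8% | 34.3% | 37.6% |
| 50% | 52.4% | 55.8% | 60.0% |

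For example, 1 − 0.70^(259/196) = 0.376.

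**Dilution.** If only half of Group 2 enters Stage 3 and all of those stay to Day 259, the group figure is 0.5 × p + 0.5 × [1 − (1 − p)^(259/196)]: 11.5%, 33.8% and 55.0% for p = 10%, 30% and 50%.

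**Serious events.** 168 + 31 = Day 199, which equals Day 196 plus the 3-day allowance. If that limit is applied, the excess for serious events is about zero. Serious and non-serious events would then cover different windows in the paired EudraCT summaries of SAP 6.9.2. If it is not applied, the serious TEAE definition has the same open end as the TEAE definition.

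**Person-time.** If no new event starts after Day 196, a rate per day for a man followed to Day 259 falls to 196/259 = 0.76 of its value. Person-time alone could therefore reverse the bias.

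**After the change.** With one cut-off at 28 days after last dose, the excess becomes 0 days and the ratio 1.00 for completers in both groups.

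**The case against.** The strongest reply is that the groups are never compared. SAP 4 and SAP 6 keep them apart, and Group 2 opens only after Group 1 has failed on efficacy, so AE percentages will not choose between them. This stands as far as formal inference goes. It does not remove the informal side-by-side reading, nor the mixture of follow-up lengths inside Group 2.

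The size is also open to challenge. Day 259 is a ceiling, reached only by men whose local T stays below 1 ng/mL to Day 252. Constant hazard is doubtful: injection site reactions are among the most frequent AEs, and no injection follows Day 168. Men on version 4.0 dilute the effect, and early withdrawals shorten follow-up in either group. All this is right, and it is why the result is a range with an upper end that may not be approached.

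A reader might go further and infer that cardiac events can be detected only at the higher dose, because Holter and cardiac biomarkers belong to Group 2. The documents do not support that.
- **Holter** is one 24-hour recording in 30 men around Day 0, and the synopsis has it analysed for arrhythmias after the whole study is complete. It can hardly drive AE reporting, and both groups have the same 12-lead ECG visits through Day 168.
- **Biomarkers:** the text conflicts. Protocol 7.2.2 has "Pre-dose blood sampling for cardiac biomarkers (Group 2 only"), and 7.2.3 to 7.2.5 repeat the restriction. The biomarker row in the joint schedule for Groups 1 and 2 and SAP 4.2.9 carry none. Under Protocol 6.3.7.1 an abnormal laboratory value must be reported as an AE only if it needs intervention or is judged clinically significant. This is a conflict to reconcile, not an established bias.

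Finally, a 28-day cut-off is shorter than the 42-day dosing interval, which after the Day 168 dose runs to Day 210. Events between about Day 200 and Day 210 would leave the main table while still inside that interval. The point is fair and shapes the fix.

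**Conclusion.** The point holds. As written, the crude TEAE percentages cover unequal windows: 14 to 63 more days for each Group 2 man in Stage 3 than for a completer without it (ratio 1.07 to 1.32). With equal daily risk, an assumed 30% becomes 31.8% to 37.6% if all men complete and enter Stage 3, and 33.8% if half do and stay to Day 259. These figures rest on an assumed incidence, a constant hazard and an assumed Stage 3 share; with few late events the inflation is small.

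The supported conclusion is that Group 2 can look worse than Group 1 through follow-up length alone. It is tempting to conclude that the higher dose will look worse, but the documents do not show that: no between-dose comparison is planned, the Stage 3 share and the timing of late events are unknown, and for serious events the 31-day limit, if applied, nearly closes the gap. The change is worth making before the tables are run.

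**What to change.** In SAP 4.2.3 and 6.9.2:

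1. Make the by-group TEAE table cover one window observed in both groups: first dose to 28 days after last dose, plus the 3-day visit allowance.
2. Tabulate Group 2 events that start later in a separate Stage 3 follow-up table. Do not label them all as off treatment, given the interval to Day 210.
3. Keep the all-TEAE table and every listing, so that no event is hidden.
4. Give person-time rates as secondary only, because they can err in the opposite direction.
5. Reconcile the 31-day SAE limit with collection for the whole trial (SAP 4.2.2) and with the open-ended serious TEAE definition, and state which dose the 31 days run from.
6. Reconcile the Group 2 restriction on cardiac biomarkers in Protocol 7.2.2 to 7.2.5 with the joint schedule and SAP 4.2.9.

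The cost is SAP wording and a few extra tables from data already collected. The downside is that late events, including those from about Day 200 to Day 210, fall outside the by-group headline percentage and must be read from the Stage 3 and all-TEAE tables. Anchoring to each man's last dose applies one rule to everyone, but it does not give equal observation time to men withdrawn early.

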AEs: All AEs will be coded using Medical Dictionary for Regulatory Activities (MedDRA) terminology and summarised by PT and SOC. Frequencies of AEs will be presented by absolute and relative frequencies of (a) the number of AEs and (b) the number of participants experiencing an event for each SOC and PT.

AEs will be summarised separately for serious AEs, treatment-emergent AEs (defined as any new or worsening pre-existing AE with a date equal to or later than the date of IMP administration) and possibly treatment-related AEs.

PK/PD: Concentrations over time will be described by area under the concentration-time curve from time zero to last available measurement (AUC_{0-t}), maximum concentration (C_{max}), time to reach maximum concentration (T_{max}), terminal half-life ($t_{1/2}$), first-order elimination rate and graphical representation of the concentrations over time. The geometric mean will be calculated additionally for AUCs and C_{max} .

Depending on the progression of the concentrations, multiple peaks of concentrations can occur. Additional AUC, T_{max} and C_{max} will be specified accordingly (total and separated by each phase of concentration increase) for the parameters.

Missing data will not be substituted in general, but in the case of a laboratory reporting concentrations as unquantifiably low, they will be set to 0.

All study data will be reported in participant data listings.

Detailed statistical methodology, definitions and data handling will be described in a separate statistical analysis plan (SAP) prior to analysis.

Responsibilities

Sponsor's Responsible Representative:	[name]
The second secon	VP Women's Health & Clinical Operations
	Antev Limited
	[name]
	London
	[name]
	UK
	Email: [contact]
Sponsor's Medical Expert:	[name]
The second secon	Chief Scientific Officer
	Antev Limited
	[name]
	London
	[name]
	UK
	Email: [contact]
Medical Lead Insuvia UAB:	[name]
	Clinical Research Physician
	[name]
	[name]
	[contact]
Biometrician Quanticate International	[name]
Ltd:	Senior Statistician I
	[name]
	[name]
	Email: [contact]
Pharmacokinetic Laboratory:	[name]
	Senior Scientist Small Molecule Bioanalysis
	Drug Development Solutions
	LGC
	[name]
	Fordham Cambridgeshire
	[name]
	UK
	[contact] [name]
	Email: [contact]

ANT-1111-02, Teverelix TFA in Prostate Cancer FINAL Version 5.0, 31 May 2022 Page 16 of 84

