6.3.7 Adverse Events

All AEs, including intercurrent illnesses or pathological changes in laboratory values, must be reported and documented in detail including the time of start and end of onset and the outcome. The measures taken will be documented in the eCRF as well as intensity, relationship to study medication and seriousness of the AE.

6.3.7.1 **Definition of Adverse Events**

An AE is any untoward medical occurrence in a participant or clinical investigation participant who is administered a pharmaceutical product. This untoward medical occurrence does not necessarily have a causal relationship with the administered treatment. An AE can, therefore, be defined as any unfavourable and unintended sign (including abnormal laboratory findings), symptom, or disease that is temporally associated with the use of a medicinal (investigational) product, whether or not related to that medicinal (investigational) product. If, during treatment with an investigational product, pathological laboratory values occur which were not present before the treatment started, further clinical or laboratory tests must be

carried out until the values return to the normal range or until a plausible explanation is found (e.g. concomitant disease) for the change in the laboratory values.

Symptoms or clinically significant laboratory or instrumental (e.g. electrocardiographic) abnormalities of a pre-existing condition, such as cancer or other diseases, should not be considered an AE. However, occurrence of new symptoms, laboratory, or instrumental abnormalities, as well as worsening of pre-existing ones, are considered AEs.

Laboratory values outside the normal laboratory-specific reference range, which make an intervention necessary and/or are considered clinically significant by the investigator must be reported as AEs. If the abnormal laboratory value is a sign of a disease, only this diagnosis should be reported as an AE.

An AE is considered to be an adverse drug reaction (ADR) if a causal relationship between a medicinal product and an AE is at least a reasonable possibility.

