This category applies to those AEs which, after careful medical consideration at the time they are evaluated, are felt with a high degree of certainty by the investigator to be related to the IMP. The relationship between the IMP and an AE is considered probable if the AE:

- follows a reasonable temporal sequence after administration of the IMP
- has already been described as a side effect of the IMP
- disappears or decreases on cessation of the IMP
- cannot be reasonably explained by the participant's clinical state

Possible

This category applies to those AEs for which, after careful medical consideration at the time they are evaluated, a connection with the IMP appears improbable but cannot be ruled out with certainty. The relationship between the IMP and an AE is considered possible if the AE:

- follows a reasonable temporal sequence after administration of the IMP
- has already been described as an AE in connection with the IMP
- could also be reasonably explained by a number of other causes

Unlikely

In general, this category can be considered applicable to those AEs which, after careful medical consideration at the time they are evaluated, are judged with a high degree of certainty to be unrelated to the IMP. The relationship between the IMP and an AE is considered unlikely if the AE:

- does not follow a reasonable temporal sequence after administration of the **IMP**
- could also be reasonably explained by a number of other causes
- does not follow a known pattern of response to the IMP

Not related

This category applies to those AEs which, after careful consideration, are clearly and incontrovertibly due to causes other than the IMP (intercurrent disease, worsening of study indication/lack of efficacy, concomitant disease, concomitant therapy, other).

Intensity

Regardless of the classification of an AE as serious or non-serious (see below), its intensity must be assessed according to medical criteria alone using the Common Terminology Criteria for Adverse Events (CTCAE) classification (v5.0):

Grade 1 (mild): asymptomatic or mild symptoms; clinical or diagnostic

observations only; intervention not indicated

minimal, local or non-invasive intervention indicated; limiting **Grade 2 (moderate):**

> age-appropriate instrumental activities of daily living (e.g. preparing meals, shopping, using the telephone, managing

money, etc.)

Grade 3 (severe): severe or medically significant but not immediately life-

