An AE is an adverse drug reaction (ADR) if a causal relationship between a medicinal product and an AE is at least a reasonable possibility. An AE will be classified as related to study medication if the relationship to study medication was recorded (on the 'Study Adverse Events' CRF page,) as 'Unlikely', 'Possible', 'Probable', 'Related'. An AE will be classified as unrelated to study medication if the relationship to study medication was recorded as 'Unrelated'.

Any AE that leads to discontinuation of treatment will have 'Action Taken with Study Treatment' reported as 'Drug Withdrawn' on the 'Adverse Event' page.

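### SAP 4.2.3 counts adverse events rated Unlikely as related to study medication, against the protocol's definition of that rating and without a stated reason

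*SAP*

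**What the plan says.** SAP 4.2.3 lists five relationship ratings: Related, Probable, Possible, Unlikely and Not related. It then reduces them to two classes. An AE is related if the rating was recorded "as 'Unlikely', 'Possible', 'Probable', 'Related'. An AE will be classified as unrelated to study medication" only if the label is Unrelated. SAP 6.9.2 points to this definition for the separate summary of treatment-related AEs, and also places treatment-related AEs in the single AE overview.

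Protocol 6.3.7.2 tells investigators what the ratings mean:

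- **Possible:** "a connection with the IMP appears improbable but cannot be ruled out with certainty".
- **Unlikely:** events that "are judged with a high degree of certainty to be unrelated to the IMP". The first listed criterion is that the event "does not follow a reasonable temporal sequence after administration of the" IMP.
- **Not related:** events that "are clearly and incontrovertibly due to causes other than the IMP".

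Two other texts bear on the cut. Protocol 6.3.7.1 and SAP 4.2.3 (in the sentence directly before the classification rule) both treat an AE as an adverse drug reaction "if a causal relationship between a medicinal product and an AE is at least a reasonable possibility". The protocol synopsis, under Statistical Methods, plans a summary of "possibly treatment-related AEs".

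The protocol gives no two-way split for tables. The same part of the synopsis defers such matters: "Detailed statistical methodology, definitions and data handling will be described in a separate statistical analysis plan (SAP) prior to analysis".

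**The concern.** The rating scale is the only guidance the investigator has when judging causality. An investigator who chooses Unlikely has been told that this means near-certainty that the drug was not the cause. The SAP then puts that event in the same class as Related. The table labelled treatment-related would no longer report what the investigators judged.

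The study is uncontrolled and safety is among its objectives, so the related-AE table is one of the places a reader will look for the tolerability profile. At stake is the descriptive accuracy of that table and of one row in the AE overview. Efficacy results, the enrolment-stopping rules and the overall AE, TEAE and SAE counts do not use the rule.

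**Working it through.** **1. The cut against the definitions**

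| Rating | Protocol 6.3.7.2, in short | SAP 4.2.3 class | Class the definition suggests |
|---|---|---|---|
| Related | definite link | related | related |
| Probable | link highly likely | related | related |
| Possible | improbable, not excluded | related | related |
| Unlikely | nearly certain there is no link | related | not related |
| Not related | other cause beyond dispute | unrelated (label differs) | not related |

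The SAP classes 4 of the 5 levels as related; the definitions suggest 3 of 5. Only the Unlikely row differs. Uncertain links already have a home in Possible.

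**2. Is a reason given elsewhere?** SAP 5.3.2.3 has a worst-case rule, but it applies when intensity or causality is missing, not when Unlikely has been recorded. SAP 4.2.3, 6.9.2 and 7.1 give no rationale.

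**3. How the excess is counted.** Let the excess be the count under the SAP rule minus the count under the 3-of-5 rule.

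- Events: excess = number of AEs rated Unlikely.
- Subjects per preferred term: SAP 4.2.3.1 keeps the strongest rating, so excess = subjects whose strongest rating for that term is Unlikely. Over all terms this cannot exceed the event excess.
- Subjects in the overview: excess = subjects with at least one Unlikely AE and none rated Possible, Probable or Related, and none with missing causality (SAP 5.3.2.3 imputes missing as related). This assumes that the overview uses the 4.2.3 definition, the only one in the SAP.

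Invented data (not trial data) show the three counts. Subject A has headache, Unlikely, twice. Subject B has headache Unlikely, headache Possible and nausea Unlikely. Subject C has rash Unlikely and hot flush Related.

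| | Events | Subject-term pairs | Subjects |
|---|---|---|---|
| SAP rule | 7 | 5 | 3 |
| 3-of-5 rule | 2 | 2 | 2 |
| Excess | 5 | 3 | 1 |

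**4. Size per subject in the overview row.** SAP 5.1.2 divides by the number of subjects in the arm. Planned enrolment is about 24 and 60 (protocol 3.1), used here as a stand-in for the numbers treated.

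- Group 1: 1/24 = 4.2 percentage points.
- Group 2: 1/60 = 1.7 percentage points.

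The documents give no count of Unlikely AEs. As an assumed range only, 1 to 3 such subjects of 24 would add 4.2 to 12.5 points (3/24 = 12.5%), and 1 to 6 of 60 would add 1.7 to 10.0 points (6/60 = 10.0%).

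**The case against.** The best defence is that a table cut is not a rating. Investigators still use five levels, the SAP only groups them, and the protocol hands definitions to the SAP. Only Not related excludes the drug beyond dispute, so counting everything not excluded is a coherent and cautious choice. Possible and Unlikely also share a criterion, that several other causes could explain the event. The AE listings and the reported investigator ratings let a reader regroup, and the output shells, which are not among the documents, may already show counts by level.

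Much of this stands. The sponsor is entitled to set the cut, the direction is cautious, and no between-arm comparison is distorted because the groups are analysed separately. It does not remove the conflict with the definition of Unlikely. The SAP nowhere says that caution is the reason, and the causality caution it does state is limited to missing data.

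A reader might infer that the rule contradicts three texts: the Unlikely definition, the drug-reaction threshold and the synopsis wording. Only the first conflicts directly. The threshold defines an adverse drug reaction, and SAP 6.9.2 plans no table of those. The synopsis phrase is loose and need not mean the rating Possible and above. Both point towards a cut at Possible, but neither sets one.

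Nor does the silence of SAP 7.1 prove an undeclared change. With no two-way split in the protocol, it is unclear that there was a change to declare.

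**Conclusion.** The point holds. SAP 4.2.3 assigns Unlikely to the related class against the protocol's definition of that rating, sits badly with two neighbouring texts, and gives no rationale. It should be corrected, but it is a reporting matter of limited reach.

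The size cannot be stated from the documents. It is zero if no AE is rated Unlikely; otherwise each subject counted solely on that rating moves the overview row by 4.2 points (of 24) or 1.7 points (of 60). These steps assume that planned enrolment is reached and that the overview uses the 4.2.3 rule; smaller arms would make each step larger.

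Two stronger inferences are not supported. The first is that the rule hides harm: it can only raise the related count. The second is that AEs rated Not related will drop out of both classes because the rule says Unrelated. That mismatch looks like a label slip, and the CRF page that would settle it is not among the documents.

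**What to change.** In SAP 4.2.3, class Possible, Probable and Related as related, together with missing causality as SAP 5.3.2.3 already provides. Class Unlikely and Not related as not related. Check the CRF label, then use one term for the lowest level throughout.

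Also show counts by the five causality levels, or show the wider grouping as a supplementary row, so that the conservative view stays visible. If the sponsor keeps the wider grouping in any table, state the reason in SAP 7.1.

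The cost is one SAP sentence, one derivation line and a CRF check, plus output-shell changes if the shells do not already carry the extra rows. The downside is a less conservative headline related count, which the by-level counts offset. If the SAP can no longer be amended, protocol 8.1.9 already requires the final study report to describe and justify such a deviation.
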